9.5.1 Primary Outcomes

1. Pearson correlation between concordance in GSR or HRV within patient-provider dyads and improvement in GERD symptom severity in the patient. Changes in GERD symptom severity will be calculated from the GERD symptom diaries collected at the first and second study visits. HRV and GSR will be measured during the visit intervention (first study visit).

We will calculate Pearson correlations between the slopes of time-locked patient and provider GSR data in 15 second intervals after smoothing. An index of concordance in GSR responses for each patient-provider dyad will be calculated as the natural logarithm of the sum of the positive correlations from the entire session minus the natural logarithm of the sum of the absolute value of negative correlations across the session [78]. Dyads with a more positive index demonstrate greater concordance, and the subjects in these dyads would be expected to demonstrate greater improvement in GERD symptom severity.

I will also perform an analysis using a similar approach to analyze the HRV data – comparing variation in the beat-to-beat intervals over short segments of time and calculating Pearson correlation coefficients for time-locked patient and provider data for these intervals.

2. Correlation between change in GSR (or high frequency HRV) and subsequent changes in GERD symptoms. We will calculate absolute changes in GSR, and also for high frequency HRV, within study subjects from the beginning to the end of the study visit and determine the Pearson correlation between these changes and reported changes in GERD symptom severity. As a secondary analysis, I will test whether changes in GSR and HRV are a function of baseline perceived stress and if that relationship differs between the standard and expanded visit interventions.

The average daily GERD symptom severity score is derived from the daily symptom diaries (sections 6.2.2 and 6.2.5) that subjects complete. The average daily GERD symptom severity is based on the daily sum of scores from the first three questions assessing severity of daytime heartburn, nighttime heartburn, and acid reflux averaged over a 7 day period. The change in GERD symptom severity is calculated by subtracting the average daily GERD symptom severity score during the last 7 days of the study from the average daily GERD symptom severity score at study enrollment. The GERD symptom severity score has been used in many GERD medication studies and was the primary outcome measure in my pilot study [61].

9.5.2 Secondary Outcomes

1. The difference in the frequency of supportive provider behaviors between the standard and expanded visit groups.
2. The difference in the ratings of rapport, engagement, and reciprocity between the standard and expanded visit groups.

Tool Revision History

Version: 11.0

Version Date: 5.8.2020

The number of nonverbally supportive behaviors and impression ratings of the patient-provider interaction will come from coding of video recordings of the patient provider interactions (study visit 1).

We hypothesize that the frequency/intensity of supportive provider behaviors increases as the expanded visit unfolds, compared to the standard visit, as rapport, engagement, and reciprocity between patient and provider increase. Briefly, thin slices (1.5 minutes) of video occurring near the beginning and end of the standard visit (and also a time point in the middle of the expanded visit roughly equivalent to the end of the standard visit) will be analyzed by trained coders, blinded to the study hypotheses, for the presence of 1) micro-level nonverbally supportive behaviors (e.g., friendly voice quality, leaning forward, open body posture, eye contact, nod, smile, and gestures) as well as 2) macro-level impression ratings of the interaction (e.g., rapport, engagement, reciprocity).

The PI will meet weekly with the coders to review findings and resolve areas of disagreement until greater than 80% concordance is achieved between coders. Frequency of supportive behaviors and ratings of interactions will be compared using generalized linear mixed models as appropriate for each outcome (e.g., occurrence of binary events, counts of discrete events, ordinal ratings of rapport or engagement). The models will include terms for time-point, visit group assignment, and their interaction.

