3. STUDY DESIGN

Study design: Single-center, single-blind, pilot randomized controlled trial

Primary outcomes:

- 1) Correlation between physiologic synchrony in patient-provider dyads (GSR or HRV) and improvement in GERD symptom severity.
- 2) Correlation between absolute changes in GSR within subjects over the course of the study visit and subsequent changes in GERD symptom severity.
- 3) Correlation between absolute changes in high frequency HRV within subjects over the course of the study visit and subsequent changes in GERD symptom severity.

Secondary outcomes:

- 1) The difference in the frequency of supportive provider behaviors between the standard and expanded visit groups.
- 2) The difference in the ratings of rapport, engagement, and reciprocity between the standard and expanded visit groups.

Study population:

Men and women age 21-70 with heartburn symptoms 3 or more days per week. We will enroll until we reach 24 completing subjects.

Study location:

The Clinical Research Center (CRC) at Massachusetts General Hospital (MGH), the Benson-Henry Institute (BHI) for Mind Body Medicine, or another MGH location.

Length of subject participation: 2 weeks

Length of study enrollment: 12-14 months

Groups:

- 1) Standard visit (n=8), modeled after an empathic, high quality conventional primary care visit.
- 2) Expanded visit (n=16), modeled after a visit with an integrative medicine provider

Randomization:

The randomization code will be generated by the study statistician as described below (section 4.3). The study will be single-blinded (study providers and the research team will know what the subject is receiving but the subject will not). Randomization will be

Tool Revision History

Version: 11.0

Version Date: 5.8.2020

stratified based on study provider. We anticipate 4 providers each seeing 6 subjects (2 standard visits, 4 expanded visits).

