Each study provider will participate in an orientation session to learn how to deliver the standard and expanded visit interventions. Providers will be explicitly instructed not to offer specific GERD treatment advice – either pharmacologic or non-pharmacologic. The study PI will review video recordings of the interactions to offer feedback to study providers and ensure protocol fidelity. As each study provider finishes his/her portion of the study, the PI will interview them to understand their experiences of the study, the two visit types, and their views on the doctor-patient relationship.

We do not anticipate any adverse effects as a result of this intervention.

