6.2.3 Blinding

This is a single-blinded study. Subjects will be unaware of the possibility for two different types of study visits. Study providers and staff will be aware of the study intervention delivered, but only immediately prior to the study visit to decrease the potential for introducing bias in how study staff interact with subjects during recruitment and consent. Subjects will be debriefed at the end of the Visit 2 regarding the nature of the study and the intervention that they received. Data will be analyzed in a blinded fashion, also to avoid introducing bias. Given the low-risk nature of the study, we do not anticipate a need to break the blind while a subject is enrolled.

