9. STATISTICAL CONSIDERATIONS

9.1 General Design Issues

Design: This is a pilot, proof-of-concept, single-blinded randomized controlled trial in which subjects will be randomized in a 2:1 fashion to receive either an expanded or standard visit intervention. We are including both types of visit interventions and randomizing subjects in this way to maximize our potential to measure a wide range in physiologic concordance within the patient-provider dyads so we can best assess our hypotheses.

Primary hypotheses:

1. Subjects in patient-provider dyads with higher levels of concordance in GSR or HRV (i.e., where patient and provider GSR or HRV change in concert) will demonstrate greater improvement in GERD symptom severity than subjects in patient-provider dyads with lower levels of concordance in these measures.
2. Subjects who experience physiologic changes similar to those elicited by mind-body techniques (i.e., decreased GSR and increased high frequency HRV) over the course of their visit will demonstrate greater improvements in GERD symptom severity than subjects who do not.

Secondary hypothesis:

1. As the expanded visit unfolds, providers will demonstrate significantly more patient-centered, nonverbally supportive behaviors and have higher global impression ratings of rapport, engagement, and reciprocity compared to early in the expanded visit and both early and late in the standard visit.

Primary outcomes:

1. Correlation between physiologic synchrony in patient-provider dyads (GSR or HRV) and subsequent improvement in GERD symptom severity.
2. Correlation between absolute changes in GSR within subjects over the course of the study visit and subsequent changes in GERD symptom severity.

Tool Revision History

Version: 11.0

Version Date: 5.8.2020

3. Correlation between absolute changes in high frequency HRV within subjects over the course of the study visit and subsequent changes in GERD symptom severity.

Secondary outcomes:

1. The difference in the frequency of supportive provider behaviors between the standard and expanded visit groups.
2. The difference in the ratings of rapport, engagement, and reciprocity between the standard and expanded visit groups.

Validity and reliability of outcome measures:

1. Assessment of physiologic concordance has been described by a number of groups and we will be using similar methodology [42,78].

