9.4 Interim Analyses and Stopping Rules

As this is a pilot study, the study PI will review video recordings of visit interventions as the study progresses to offer feedback to the study intervention providers. To ensure that we will have an adequate response rate to analyze our outcomes of interest, we will analyze changes in GERD symptom improvement after 6 subjects have completed the expanded visit intervention (we will not break the blind for unenrolled subjects). If there are not at least 2 subjects with a 50% or greater improvement in GERD symptoms and it is deemed that the study providers are delivering the standard and expanded interventions appropriately, we may consider protocol amendments to improve subject expectancy for symptom improvement.

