10.3.3 Monitoring

The study PI will regularly review study questionnaires, HRV and GSR data, video recordings, and logs for completeness and quality. Such review will follow each subject initially but will occur at least every 1-2 months for the duration of the study.

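### Section 9.5.2 does not confine the PI's weekly coder meetings to clips that are not analysed, so an unmasked person may influence disputed codes behind both secondary outcomes (minor).

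*Combined protocol and SAP*

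**What the plan says.** Section 9.5.2 derives both secondary outcomes (frequency of supportive provider behaviours; ratings of rapport, engagement and reciprocity) from coding of short video slices of visit 1. The slices "will be analyzed by trained coders, blinded to the study hypotheses". After describing that coding, the section continues: "The PI will meet weekly with the coders to review findings and resolve areas of disagreement until greater than 80% concordance is achieved between coders". It then moves to the mixed models.

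The hypothesis for these codes has a direction. Section 9.1 expects that, as the expanded visit goes on, "providers will demonstrate significantly more patient-centered, nonverbally supportive behaviors", and expects higher global ratings too. The comparators are early in the expanded visit and both early and late in the standard visit.

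On masking, section 3 says that "study providers and the research team will know what the subject is receiving but the subject will not". Section 5.1 adds: "The study PI will review video recordings of the interactions to offer feedback to study providers and ensure protocol fidelity". Section 9.4 repeats that "the study PI will review video recordings of visit interventions as the study progresses", and section 10.3.3, which covers the PI's checks of recordings and other data for completeness and quality, says: "Such review will follow each subject initially". Section 6.2.3 gives a general assurance: "Data will be analyzed in a blinded fashion, also to avoid introducing bias".

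**The concern.** The plan keeps the hypotheses from the coders, which shows that it regards expectation as a threat to these measurements. It then puts the person who holds the hypothesis into the meetings where coding disagreements are resolved, without saying what material is discussed. If that material is the study slices, the safeguard is weakened exactly where a code is in doubt.

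At stake is the comparison of both secondary outcomes between randomised arms of 8 and 16. Section 9.2 describes a pilot meant to pick out features for later studies. The practical harm would therefore be a wrong choice of which behaviours or ratings look worth pursuing, and a consistent tilt in the codes would not average out in a larger sample. The primary outcomes use physiologic and symptom-diary data, not video codes, and are not touched.

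**Working it through.** No formula in the plan bears on this point. The design calculations in 9.2 concern the primary correlations. The check is a comparison of passages.

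1. **Which material do the meetings cover?** Two features of the sentence in 9.5.2 pull in opposite directions. Meetings that end once agreement passes a reliability threshold look like calibration before or early in coding. The reference to findings, and the position directly after the description of slice coding, look like work on study material. The section does not mention practice clips, does not say whether independent codes are kept, does not say which codes enter the models, and does not say who settles disagreements after 80% is passed. No other section answers these questions.

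2. **Is the PI masked to the hypothesis?** No. It is stated with its direction in 9.1 and again in 9.5.2.

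3. **Is the PI masked to visit type?** The plan does not make it so. Section 3 says the research team knows it. The PI watches the recordings (5.1, 9.4, 10.3.3), at first after each subject. Section 9.3 uses the recordings to verify which intervention was delivered, so visit type can be recognised from them. The statistician's custody of the randomisation code (9.2) does not mask someone who watches the visits.

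4. **Are the coders masked to visit type or time point?** Section 9.5.2 states blinding to the hypotheses only. The hypothesis contrasts late expanded slices with the other visit-by-time cells, so both labels matter.

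5. **Which outcomes are exposed?** Both secondary outcomes. Exposure is greatest where a code is a judgement: voice quality, rapport, engagement, reciprocity. It is less for gaze, nods and smiles, for which 9.1 cites high reliability and validity.

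6. **Consequence under each reading.**
   - Study slices: someone who knows the hypothesis, and can know the arm, influences disputed codes that are then analysed.
   - Calibration only: the PI shapes a common coding standard. A shift in that standard applies to both arms and does not by itself separate them.

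7. **Can the size be bounded?** No. Agreement above 80% describes the state in which the meetings stop. Disputes handled in the meetings arise before that, at a level of agreement the documents do not give. The plan also does not say whether 80% applies to each item or overall. For ordinal ratings, a percentage of agreement does not limit how far a resolved rating may move.

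8. **Number of slices, needed only for the cost of the fix.** If standard visits give two slices and expanded visits three (an assumption from the description in 9.5.2): 8 × 2 + 16 × 3 = 16 + 48 = 64.

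**The case against.** The strongest reply is that the sentence describes ordinary coder training. A reliability target that ends the meetings is typical of calibration. Section 10.3.1, under which the PI trains and supervises coordinators and interns so that measures are collected properly, fits that picture, although it does not name the coders. This stands as a plausible reading, and on it there is little to correct beyond saying so.

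A second reply is that the plan already protects the coding. Section 6.2.3 promises blinded analysis, and 9.5.2 and 11.3 both speak of the video work as analysis, so the promise may well extend to coding. Section 11.3 also places the video analysis with an outside collaborator and labels files by participant number, so a file name need not show the arm. These passages narrow the gap. They do not close it: none mentions the resolution of disagreements, none takes the PI out of the meetings, and a participant number does not mask a PI who has already seen the recording.

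A third reply is that this is a pilot, with secondary outcomes, where masking cannot be complete because a slice's content can reveal the visit type. All of that is true. It limits the weight of the point but does not remove the reason to state the procedure.

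**Conclusion.** The point holds as a gap in specification. Section 9.5.2 leaves open a procedure in which an unmasked PI influences disputed codes behind both secondary outcomes, and it does not state that coders are masked to visit type or time point. Severity is minor: the primary outcomes are unaffected, and on the calibration reading the risk is small.

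Two stronger conclusions are tempting and are not supported. A reader might infer that the PI does settle the analysed codes and that the secondary comparisons are therefore biased. The text is equally consistent with calibration, so bias is possible but not shown. A reader might also take the 80% threshold to mean that fewer than one code in five could be affected, and build a maximum bias on that. The disagreements left once 80% is passed are not assigned to the PI, and those resolved earlier have no stated frequency. No figure for the bias should be quoted.

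A separate and smaller inconsistency touches the same comparison. Section 9.3 groups subjects by the visit they received, while the models in 9.5.2 use the assigned group. It matters only if a subject is given the wrong script, which 9.3 does not expect.

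**What to change.** In 9.5.2:

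- Limit the PI's meetings with the coders to calibration on clips that are not analysed.
- For study slices, keep each coder's independent codes, have the coders settle disagreements without the PI, and state that the settled codes are the ones analysed.
- Present slices under random labels and in random order, so that coders are masked to visit type and time point as far as content allows.

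Separately, reconcile 9.3 with 9.5.2: use randomised assignment for the between-group comparison, with visit received as a sensitivity analysis.

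The cost is a few sentences and the relabelling of about 64 slices, if expanded visits give three each. No staff are added. Codes may be slightly noisier without the PI's input, and masking will remain incomplete.

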Once enrolled, subjects will be randomized to receive either the standard visit intervention (n=8) or the expanded visit intervention (n=16; section 9.2). They will not know that there are two possible visit choices. This aspect will be revealed to subjects during a debriefing at the follow-up visit. We will stratify by provider and create permuted block sizes of 3 and 6 (2 expanded, 1 standard; 4 expanded, 2 standard) with the intent to enroll 4 providers who will each see 6 subjects. If we can only enroll 3 providers or one provider cannot see 6 subjects then the remaining slots will be divided among the remaining providers.

Provider Recruitment and Screening:

We will approach pre-identified MGH internal medicine physicians and ask whether they are interested in participating in the study as providers. If we cannot identify enough interested physicians internally, we may approach colleagues at other Partners-affiliated institutions and/or send an email describing the study to internists within the MGH Division of General Internal Medicine. We may also present the study at practice meetings or division conferences. Providers must be willing to adhere to the study protocol and not provide specific treatment recommendations (pharmacologic or non-pharmacologic) as this is outside the scope of the study and subjects must remain on a stable regimen during the course of the study. Providers must also be willing to receive a brief training to understand how to deliver the standard and expanded visit interventions.

Provider Consent:

Participating providers will be consented by the study PI. As study providers will deliver both visit interventions, they will not be blinded as to the study's hypotheses or the group to which a given subject is assigned. They will be notified of which intervention they are delivering immediately before walking into the room to conduct the study visit.

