- Perceived Stress Scale (PSS) – a widely used 10 item measure of perceived stress that has been shown to correlate with a variety of different health outcomes [72]. Study providers will complete this questionnaire immediately prior to each study subject visit.

Tool Revision History

Version: 11.0

Version Date: 5.8.2020

- Fatigue Scale – 1 item self-report measure of the current fatigue level on a scale of 0 (no fatigue) to 10 (extreme fatigue). Study providers will complete this question immediately prior to each study subject visit.

Randomization

Subjects will be randomized on the day of their baseline visit (Visit 1), following consent, to receive either the standard or expanded visit with the particular provided that they are scheduled to see that day. We will stratify randomization by provider so that each provider does the same proportion of standard and expanded visits. Randomization will occur after subjects have completed their optional first blood draw and baseline questionnaires, immediately prior to the study visit. Study providers will open an envelope instructing them which study visit intervention to deliver.

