9.2 Sample Size and Randomization

This is a pilot study whose aim is to identify features on which to focus in subsequent studies. For the primary outcome, we would consider an observed correlation greater than $r = 0.20$ adequate evidence of a positive association worthy of further investigation. With a sample size of 24 patient-provider dyads, the study will have an 80% probability of obtaining an estimated correlation between physiologic concordance and changes in GERD symptoms (our primary outcome) greater than $r = 0.20$ if the true correlation is at least $\rho = 0.36$. The study will have 80% power to declare the correlation significantly greater than zero based on a two-sided $\alpha = 0.05$ if the true correlation is at least $\rho = 0.54$.

Treatment Assignment Procedures

A randomization scheme will be devised before the start of the study by the study biostatistician who will retain the code and will be responsible for breaking the blind at the end of the study. We do not anticipate a need to break the blind during the study because

Tool Revision History

Version: 11.0

Version Date: 5.8.2020

we are not expecting serious adverse events to occur more frequently in one visit group than another. Randomization will be stratified by provider, with a goal to have 4 providers each see 6 subjects (4 expanded and 2 standard visits each). If a provider cannot commit to this many visits, the study biostatistician may need to adjust the randomization scheme.

The study biostatistician will create numbered envelopes that will indicate which intervention is to be delivered. After a subject has consented to participate in the study, while he or she is completing the baseline questionnaires, immediately prior to the actual visit intervention, the envelope corresponding to the enrolled subject will be opened to reveal which intervention is to be delivered.

If a subject drops or is unable to complete the study, the statistician may need to rebalance the randomization scheme within a stratum.

Subjects will be informed of their “treatment” assignment during a debriefing at the end of the second study visit.

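### The section 9.5.2 mixed models name no random effect and leave out provider, the randomisation stratum, so the analysis of provider behaviour is under-specified and may lose precision

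*Combined protocol and SAP*

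**What the plan says.** Section 9.5.2 gives the model class: "Frequency of supportive behaviors and ratings of interactions will be compared using generalized linear mixed models as appropriate for each outcome". It then gives the content: "The models will include terms for time-point, visit group assignment, and their interaction". The outcomes table in section 9.5 repeats the model class and adds no term. Neither place names a random effect, for subject or for provider, and section 9.6 does not fill the gap.

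Provider is built into the design. Section 3: "We anticipate 4 providers each seeing 6 subjects (2 standard visits, 4 expanded visits". Section 6.2.2: "We will stratify randomization by provider so that each provider does the same proportion of standard and expanded visits". Section 4.3 allows for fewer or uneven strata: "If we can only enroll 3 providers or one provider cannot see 6 subjects then the remaining slots will be divided".

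The comparisons of interest are mostly between visit groups. Under the secondary hypothesis in section 9.1, late expanded visits are to score higher "compared to early in the expanded visit and both early and late in the standard visit", so two of its three comparisons cross the groups. Section 9.5.2 also codes "a time point in the middle of the expanded visit roughly equivalent to the end of the standard visit", which sets up a further between-group comparison.

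**The concern.** About four people generate all of the provider behaviour that is coded, and habits such as nodding, smiling or leaning forward may differ between them. Randomising within provider removes those differences from the visit-group comparison, but the standard error shows the benefit only if the model contains provider. Otherwise the provider differences stay in the residual and the interval is wider than the design requires.

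Each visit also yields two or three coded slices. A model with no subject (dyad) effect would treat slices from one visit as independent. For the average group difference that error runs the other way, towards false positives. As written, 9.5.2 does not tell the analyst which of these models to fit, so the choice could be made after the data are seen.

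**Working it through.** **The plan's own figures.** None are given for 9.5.2. Those in section 9.2 concern the primary correlations, and they reproduce. With Fisher's z, SE = 1/√(24 − 3) = 0.2182.

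- Power at ρ = 0.54: Φ(0.6042/0.2182 − 1.96) = Φ(0.809) = 79.1% (simulation 80.8%).
- Chance of r > 0.20 at ρ = 0.36: Φ((0.3769 − 0.2027)/0.2182) = Φ(0.798) = 78.8% (simulation 80.1%).

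**Inputs.** From the documents: 24 dyads, as 4 providers × (4 expanded + 2 standard). Slices are read as two per standard and three per expanded visit, so 8×2 + 16×3 = 64 in all and 2×2 + 4×3 = 16 per provider; that reading is an assumption. Also assumed, because the documents give no values: provider ICC 0 to 0.5, dyad ICC 0.2 to 0.6, provider-by-visit variance 0.1 to 0.2 (total variance about 1), and a 1 SD group effect for power.

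**Step 1: provider left out, subject clustering handled.** Take one normal score per dyad, such as the late slice. The 4:2 split is the same for every provider, so provider effects cancel from the group difference but stay in the residual. With provider ICC = c, the residual sum of squares on 22 df has expectation 22(1 − c) + 18c (3 provider df × 6 dyads = 18). Hence:

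SE ratio (with/without provider) = √[(1 − c)/(1 − c + c·18/22)], and CI ratio = SE ratio × t19/t22 = SE ratio × 2.093/2.074 = SE ratio × 1.009.

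| Provider ICC | SE ratio | CI ratio | CI change, simulated | Error of 5% test without provider | Power at 1 SD, without → with |
|---|---|---|---|---|---|
| 0 | 1.000 | 1.009 | 0.8% wider | 5.0% | 60% → 59% |
| 0.1 | 0.957 | 0.966 | 3% narrower | 4.2% | 61% → 64% |
| 0.3 | 0.860 | 0.868 | 13% narrower | 2.8% | 64% → 74% |
| 0.5 | 0.742 | 0.748 | 24% narrower | 1.6% | 68% → 87% |

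At ICC 0.5 the formula gives 25%. The simulated mean SEs, 0.403 and 0.302, give 0.302/0.403 × 1.009 = 0.756, or 24%. With provider in the model the error is 4.8% to 5.0%.

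Other settings, at provider ICC 0.1, 0.3, 0.5 unless stated:

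- Three providers split 9/9/6: error 4.3%, 3.1%, 2.1% without provider; CI 3%, 12%, 22% narrower with it.
- Counts, mean 5 per slice, ICC 0.12, 0.36, 0.56: error 3.5%, 2.5%, 1.5%; CI 5%, 16%, 26% narrower.
- Provider as a random intercept: CI 5%, 14%, 25% narrower than with no provider term; error 5.0% to 5.5%.

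**Step 2: contrasts over time.** Early-versus-late differences within a visit cancel the provider effect. With subject clustering in the model, the time-by-group contrast has 5.0% error with or without provider, and the CI is 0.7% wider with it.

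**Step 3: no subject effect.** With dyad ICC = d, the true variance of the average group difference is d(1/16 + 1/8) + (1 − d)(1/48 + 1/16) = 0.1875d + 0.0833(1 − d). An analysis of independent slices uses 0.0833. The ratio is 1 + 1.25d, or 1.25, 1.50, 1.75 at d = 0.2, 0.4, 0.6. The error is then P(|Z| > 1.96/√ratio) = 8.0%, 11.0%, 13.8%. Simulation gave 7.9%, 10.9%, 14.2%. The interaction test goes the other way: 3.0%, 1.2%, 0.3%.

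**Step 4: visit effect differs between providers.** At provider-by-visit variance 0.1 to 0.2 and provider ICC 0 to 0.5, simulated error with provider fixed is 6.0% to 9.6%. Without provider it is 2.5% to 6.6%.

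**Step 5: sparse binary behaviours.** The chance that at least one of four providers shows no event in 16 independent slices is 1 − [1 − (1 − p)^16]^4. At p = 5%, 10%, 20% this is 90%, 56%, 11%. A fixed provider effect is not estimable on the logit scale for such a provider.

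**The case against.** The strongest reply is that omission is not shown. The models are called mixed, so some random effect is intended, and the sentence on terms reads naturally as the list of fixed effects. If the unnamed random effect is provider, most of the gain in Step 1 is already obtained. That stands: the documents show under-specification and do not show that provider or subject will be ignored.

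Second, the larger gains need a provider ICC of 0.3 to 0.5, which nothing in the documents supports. Providers follow a script, are told in section 5.1 to keep empathy equal in both groups (including eye contact, a coded behaviour), and receive feedback from video review. At ICC 0.1 the gain is 3%. That also stands.

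Third, a provider intercept is not free. Step 4 shows that it can make the test mildly liberal when the visit effect varies by provider. The calculations cover normal scores and counts; ordinal ratings, which include rapport and engagement, were not simulated. Both are real limits.

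A reader might infer that leaving out provider inflates false positives for the secondary outcomes. Under the conditions of Step 1 it does the opposite, because provider is crossed and balanced with visit type. Inflation arises from a missing subject effect, or can arise from a varying visit effect, neither of which the documents establish.

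**Conclusion.** The gap is real and minor. Section 9.5.2 should say which random effects are fitted and how provider enters. Provided that slices are clustered by subject and the visit effect is similar across providers, the cost of leaving out provider is conservatism and CI width, at the sizes in the Step 1 table. Without those two provisos, valid but conservative cannot be assumed. These are secondary outcomes of a pilot with no stated power for them.

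A reader might also infer that the primary Pearson tests and the 80% figures in 9.2 are undermined because dyads share providers. The documents do not support that. The figures reproduce, and the test is inflated only if both concordance and symptom improvement cluster by provider. Improvement is the patient's own diary score, and providers may not give treatment advice. At assumed ICCs of 0.1 to 0.3 for concordance and 0.05 to 0.1 for improvement, error is 5.2% to 6.6%, and the chance of passing r > 0.20 with no true correlation is 17.7% to 19.0% against 17.4%. Error reaches 9% to 14% only at an improvement ICC of 0.3. No change to 9.5.1 or 9.2 follows.

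**What to change.** In 9.5.2, state for each model:

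1. Fixed effects: time-point, visit group, their interaction, and provider.
2. A random intercept for subject (dyad).
3. For sparse binary behaviours, provider as a random intercept in place of the fixed effect, under a threshold set in advance (for example, any provider with no events).
4. A descriptive display of the visit-group difference by provider, so that a visit effect that varies between providers is visible.

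**Cost.** Wording only, no patients. The fixed effect uses 3 df with four providers (2 with three), or about a 1% wider CI if providers do not differ. For behaviours seen in 5% to 10% of slices the fallback will often apply (Step 5). If the visit effect varies between providers, the adjusted test has about 6% to 10% error against about 3% to 7% without provider, which is why item 4 belongs in the text. In one setting with strongly clustered counts (mean 10, ICC 0.65), the provider-adjusted quasi-Poisson test had 6.4% error.
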